6.1.1 Study Definitions

6.1.1.1 Definition of Study Days

Study Day 1 is defined as the date on which the patient is administered the first dose of any study drug.

Other study days are defined relative to the Study Day 1 with Day 1 being Study Day 1 and (Day - 1) being the day prior to Study Day 1.

6.1.1.2 Definition of Study Cycle

The starting date of a new cycle is the date on which the dose of modakafusp alfa is administrated.

6.1.1.3 Definition of Study Visit Window

All data will be categorized on the basis of the scheduled visit at which they are collected. These visit designators are predefined values that appear as part of the visit tab in the electronic case report form (eCRF). The analysis of PK data will be based on the actual elapsed time post dose.

6.1.2 Analysis Approach for Continuous Variables

Continuous variables will be summarized by dose level by phase using summary statistics including mean, standard deviation, median, first and third quartiles.

6.1.3 Analysis Approach for Binary Variables and Categorical Variables

For binary and categorical variables, frequency and percentage will be provided by dose level by phase. The 2-sided 95% CI will be calculated based on Clopper-Pearson method (exact method) ([Clopper, C., Pearson, E.S, 1934](#)). No formal statistical comparisons will be performed between dose levels.

6.1.4 Analysis Approach for Time-to-Event Variables

Time to event endpoints will be estimated using the Kaplan-Meier (K-M) method (Kaplan, E.L, Meier, P., 1958). The K-M curves, the 25th, 50th (median) and 75th percentiles, alone with associated 2-sided 95% CIs based on Brookmeyer and Crowley method ([Brookmeyer, R., Crowley, J., 1982](#)). The K-M probability estimates with 95% CIs at appropriate times will be presented if data permits. The number of patients with events and the number of patients

censored will be summarized. No formal statistical comparisons will be performed between dose levels.

6.2 Disposition of Subjects

Study information, including the date first subject signed informed consent form (ICF) for each phase, date of first subject dosed (for phase 1 dose escalation portion), date of last subject dosed (for phase 1 dose escalation portion), date of first subject randomized (for phase 2a dose finding portion), date of last subject randomized (for phase 2a dose finding portion), date of last subject's last visit/contact, date of last subject's last procedure for collection of data for primary endpoint(s), data cut-off date for analysis, MedDRA version, NCI CTCAE version, WHO Drug version, and SAS version will be presented in listings.

Screen failures as well as reasons will be summarized.

Patient disposition will be summarized using counts and percentage of patients based on all enrolled patients. The disposition will include the following categories:

- Treatment status (never treated (only applicable for phase 2a portion), ongoing, discontinued treatment)
 - Reasons for discontinuation of treatment
- Study status (discontinued from study, ongoing in study)
 - Reason for discontinuation of study
- Participating in PFS follow-up
- Participating in OS follow-up

The number and percentage of subjects in each population will be summarized.

A table and listing of significant protocol deviations will be presented.

6.3 Demographic and Other Baseline Characteristics

6.3.1 Demographics

All demographics will be summarized based on the safety population using descriptive statistics. Demographic data to be evaluated will include, but not limited to, age, sex, race, ethnicity, height, and weight.

6.3.2 Medical History and Concurrent Medical Conditions

Medical history and concurrent medical conditions will be coded using the most recent version of MedDRA available at the time of coding. Concurrent medical conditions are the ones ongoing or started on or after the day informed consent is signed. Medical history and concurrent medical conditions will be summarized separately based on safety population by System Organ Class (SOC) and Preferred Term (PT) using counts and percentages.

If both start date and stop date are missing, medical condition will be assumed to start before informed consent and continue after treatment discontinuation. If only start date is missing, then

medical condition will be assumed to start before informed consent. If stop date is missing, then medical condition will be assumed to continue after treatment discontinuation.

6.3.3 Baseline Characteristics

Baseline characteristics will be summarized using descriptive statistics based on the safety population. The characteristics include the following:

Disease characteristics:

- Years since initial diagnosis [(date of first dose – date of diagnosis) / 365.25].
- Type of Myeloma
 - IgG, IgA, IgD, IgM, Biclonal (if known, otherwise summarize with Light chain below).
 - Light Chain Kappa, Light Chain Lambda, Light chain Biclonal, Light Chain unknown.
- Measurable disease
 - Measurable by both SPEP (baseline serum M-protein ≥ 0.5 g/dL) and UPEP (baseline urine M-protein ≥ 200 mg/24 hr)
 - Measurable by SPEP only
 - Measurable by UPEP only
 - Measurable by FLC only (met all three criteria below):
 1. Involved either Kappa or Lambda free light chain level at baseline ≥ 10 mg/dL;
 2. and FLC ratio (Kappa FLC/Lambda FLC) is abnormal (serum FLC ratio > 1.65 or < 0.26)
 3. and not measurable by SPEP or UPEP
- International Staging System (ISS) at study entry.
- Revised ISS (R-ISS) at study entry.
- Evidence of Lytic Bone Disease at initial diagnosis.
- Evidence of Extramedullary Disease at initial diagnosis.
- Eastern Cooperative Oncology Group (ECOG) performance status.

Baseline disease characteristics – laboratory values

- β_2 -microglobulin category (< 2.5 , $2.5-5.5$, > 5.5 mg/L).
- Serum albumin category (< 3.5 , ≥ 3.5 mg/dL).
- Serum creatinine category (≤ 2 , > 2 mg/dL).
- Calculated creatinine clearance category (< 30 , $30 - < 60$, $60 - < 90$, ≥ 90 mL/min).

Creatinine clearance will be calculated using the Cockcroft-Gault formulas as follows:

For male patients:

$$\text{creatinine clearance} = \frac{(140 - \text{Age[yrs]}) \times \text{weight[kg]}}{72 \times (\text{serum creatinine [mg/dL]})}$$

For female patients multiply by 0.85.

- Hemoglobin (g/L).
- Platelet count ($10^9/L$).
- Absolute neutrophil count ($10^9/L$).
- Lactate dehydrogenase (LDH) > Upper limit of normal (ULN).

Baseline Bone Marrow Evaluation

- Baseline bone marrow aspirate/biopsy performed and adequate for interpretation.
- Percent plasma cells in bone marrow (if both biopsy and aspirate were performed use larger value; unable to detect is considered as zero).

Cytogenetics

- Cytogenetic testing performed.

The number and percentage of patients with each type of chromosomal aberration or abnormality will be presented including but not limited to the following:

- high risk cytogenetics [del 17, t(4;14) or t(14;16)].
- expanded high risk cytogenetics [del 17, t(4;14), (14;16), or 1q21 amplification/gain].
- del 17.
- t(4:14).
- t(14:16).
- 1q21 amplification/gain.

(percentages are based on the number of patients with cytogenetic testing performed)

Extramedullary Disease Assessment (imaging)

- Imaging lytic lesions (yes, no, indeterminate).
- Imaging extramedullary plasmacytomas (yes, no, indeterminate).
- Location of plasmacytomas.
- Number of plasmacytomas (1, 2, ≥ 3).
- Skeletal survey results (normal, abnormal not clinically significant, abnormal clinically significant, and not done).
- Skeletal survey lytic lesions (yes, no, indeterminate).

Prior therapy

- Prior radiation (yes, no).
- Prior surgery (yes, no).
- Prior bone marrow transplant or stem cell transplant.

- Type of stem cell transplant (autologous, allogeneic, syngeneic, unknown).
- Prior systemic therapy (yes, no).
- Lines of prior therapy (descriptive statistics and categorical summary: 1, 2, 3, 4, 5, 6, >6).
- Lines of prior therapy initiated within 12 months of first dose of modakafusp alfa (categorical summary).
- Type of prior therapy may include (if data permits) but not limited to:
 - Anti-CD38 monoclonal antibody (i.e. Daratumumab, Isatuximab).
 - CAR-T.
 - Anti-BCMA.
 - T-Cell engager.
 - IMiD.
 - Proteasome inhibitor (PI).
 - Anti-SLAMF7 (i.e. Elotuzumab).
- Type of last line of prior therapy.
- Best response to any prior anti-CD38.
- Best response to last line of prior therapy
- Refractory to prior therapy may include but not limited to:
 - Refractory to BCMA agents.
 - Refractory to anti-CD38.
 - Refractory to IMiD.
 - Refractory to PI.
 - Refractory to IMiD and PI.
 - Refractory to IMiD, PI, and anti-CD38.
 - Refractory to last line of prior therapy.

Refractory to therapy is defined as: best response of the treatment is stable disease or disease progression on treatment or date of progression is no more than 60 days from the end date of the last agent (start date to be imputed where only year or month/year are entered).

6.4 Medication History and Concomitant Medications

Medication history and concomitant medications will be coded using the latest World Health Organization (WHO) Drug Dictionary.

If both start date and stop date are missing, medication will be assumed to start before the first dosing date of the study drug and continue after treatment discontinuation. If only start date is missing, then medication will be assumed to start before the first dosing date of the study drug. If

only stop date is missing, then medication will be assumed to continue after treatment discontinuation.

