6.4.1 Prior Therapy

Prior medication is defined as the anticancer medication stopped before the date of first dose of any study drug. Prior medication will be coded by preferred term using the latest World Health Organization (WHO) Drug Dictionary.

The safety population will be used for the analysis of prior therapy.

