6.4.2 Concomitant Medications

Concomitant medication is defined as the medication ongoing at the time of the first dose of any study drug or medications started on or after the first dose of any study drug. Concomitant medications will be coded using the latest WHO Drug Dictionary. The number and percentage of patients taking concomitant medications will be tabulated by Anatomical Therapeutic Chemical (ATC) classification pharmacological subgroup and WHO standardized medication name.

The safety population will be used for the analysis of concomitant medications.

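### SAP 6.4 treats every medication with a missing stop date as continuing past study treatment, so a previous myeloma drug with a blank stop date is reported as concomitant instead of prior

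*SAP*

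**What the plan says.** Four parts of the SAP bear on this.

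- **Section 6.4** gives one set of missing-date rules for medication history and concomitant medications. If "only stop date is missing, then medication will be assumed to continue after treatment discontinuation". The rule for two missing dates has the same effect at the stop end: "If both start date and stop date are missing, medication will be assumed to start before the first dosing date of the study drug and" to run on past the end of treatment. Neither rule makes an exception for anticancer drugs.
- **Section 6.4.1**, which sits under 6.4: "Prior medication is defined as the anticancer medication stopped before the date of first dose of any study drug".
- **Section 6.4.2**, also under 6.4: "Concomitant medication is defined as the medication ongoing at the time of the first dose of any study drug", or started on or after it. Anticancer drugs are not excluded.
- **Section 6.3.3** defines refractory status by best response, or by a date test: "date of progression is no more than 60 days from the end date of the last agent". Its only imputation note is "start date to be imputed where only year or month/year are entered". It does not refer to 6.4. The same section separately tabulates "Lines of prior therapy (descriptive statistics and categorical summary: 1, 2, 3, 4, 5, 6, >6") and types of prior therapy.

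In the protocol, section 7.1 criterion 8 sets minimum intervals between earlier treatment and first dose: 14 days for chemotherapy (including PIs) and IMiDs, and the longer of 28 days or 5 half-lives for antibody-based therapy. Section 9.5.2 asks sites for start and stop dates and best response for each earlier regimen, and for refractoriness under IMWG criteria.

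**The concern.** Assuming that a drug with no stop date is still being taken is a sensible default for ordinary concomitant medication. It is the wrong default for a drug the site has recorded as earlier myeloma treatment, because the washout requires that drug to have ended before first dose. Applied as written, the rule removes the drug from the 6.4.1 table and shows it as an active myeloma drug alongside study treatment.

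The refractory definition has a related gap. Its date test depends on an end date and a progression date, yet the only imputation it mentions is for the start date, which the test does not use. A programmer who meets a blank end date will find just one missing-stop-date rule for medications in the SAP, the one in 6.4.

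Prior exposure and refractoriness define who is enrolled in both phases, so readers will look closely at these tables.

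**Working it through.** No figure stated in either document depends on this rule, so there is nothing to reproduce. The check applies the definitions as logic.

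**Step 1: prior or concomitant.** Let S be the stop date and F the date of first dose.

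- 6.4: S missing, so S is taken to fall after treatment discontinuation, which means S > F.
- 6.4.1: prior requires S < F. Fails.
- 6.4.2: concomitant requires the drug to be ongoing at F. Met.
- Protocol criterion 8: for the listed drug classes, S must precede F by the stated interval. The imputed S contradicts this for any eligible patient.

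**Step 2: the 60-day test.** Let P be the progression date and take the interval as signed, P − S, so that progression while still on the drug counts. The test is P − S ≤ 60 days. If the 6.4 date were used, then S > F > P for any progression before first dose, so P − S < 0 and the test is met whatever the true stop date.

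**Step 3: an illustrative record.** All dates are assumed: F = 1 June 2023, P = 1 April 2023, true S = 1 October 2022, and an imputed S of 2 January 2024 to stand for a date after treatment ended.

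| Stop date used | Prior (6.4.1) | Concomitant (6.4.2) | P − S | 60-day test |
|---|---|---|---|---|
| True date | yes | no | +182 days | not met |
| Missing, imputed under 6.4 | no | yes | −276 days | met |
| Missing, not imputed | cannot be decided | cannot be decided | undefined | cannot be decided |

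The middle row's change in the prior and concomitant columns follows from the text. Its change in the 60-day column needs the further assumption that the 6.4 date is carried into 6.3.3.

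**Step 4: size per affected patient.** One patient moves a percentage by 100/n points: 100/20 = 5.0 in a phase 2a arm of 20, and 100/18 = 5.6 among 18 phase 1 patients. The number of affected patients cannot be derived, because neither document gives a rate of missing stop dates.

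**The case against.** The strongest reply is that this will seldom arise and changes little when it does. The protocol asks for stop dates for every earlier regimen (9.5.2) and runs logic checks and queries for missing data (12.1), so wholly blank stop dates should be uncommon. Baseline and prior-therapy summaries are descriptive, and the protocol rules out inferential statistics for them (13.1.2). All of that stands, and it limits the size of the problem. It does not make the rule give the right answer when a stop date is blank.

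A reader might infer more than the documents support:

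- **That prior exposure disappears from the report.** It does not. The 6.3.3 counts of lines and drug types are not defined by stop date, so the shown effect is confined to the 6.4.1 and 6.4.2 tables.
- **That the SAP labels these drugs refractory.** It does not say so. 6.3.3 does not cite 6.4, one limb of the definition rests on best response and needs no end date, and refractoriness is also collected directly. Lenalidomide in phase 2a could not be falsely labelled in any case, since criterion 5b requires every patient to be refractory to it.
- **That the anti-CD38 subgroup of ORR is distorted.** The subgroup has only naive and sensitive categories, so a patient wrongly called refractory would fit neither. This again needs the carry-over, and the SAP does not say the subgroup is derived from the 60-day test.
- **That patients would be counted as major protocol deviators.** Major deviations come from a list the sponsor maintains (SAP 5.4), not from imputed dates in a medication table.
- **That a given share of patients is affected.** Any such percentage would need a missing-date rate and a number of drugs per line that neither document supplies.

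**Conclusion.** The concern holds in a limited form. Sections 6.4, 6.4.1 and 6.4.2 read together state a rule that gives a wrong result: a previous myeloma drug with a blank stop date is moved from the prior-therapy table to the concomitant table, against the protocol's own washout. This follows from the text and applies to either phase. The only assumption is that the patient met criterion 8.

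The refractory point is a gap, with a conditional consequence. 6.3.3 has no rule for a missing end or progression date. If the 6.4 date were used, and the interval is signed, every pre-study progression would meet the 60-day test; if it were not used, the test could not be decided.

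The reach is the descriptive prior-therapy and concomitant tables and possibly the refractory tables, at 5.0 or 5.6 percentage points per affected patient with denominators of 20 or 18. How many patients are affected is unknown. Overall ORR, DLT and TEAE analyses and the sample size do not change. It should be corrected because the rule is wrong as stated and the correction is cheap.

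**What to change.** **Section 6.4.** Limit the assumption of continuation to medications that are not recorded as prior anticancer therapy. State that an agent recorded as prior anticancer therapy is classed as prior whether its stop date is missing or partial, and that no specific stop date is imputed for washout checks. A date set close to first dose could itself look like a breach of the 14-day or 28-day intervals in criterion 8.

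**Section 6.3.3.** Keep the note on start dates, because the same section also reports lines begun within 12 months of first dose. Add that where the end date or the progression date is missing, or too incomplete to decide the 60-day test, the IMWG refractory status collected at screening is used; if that is unavailable, the status is reported as unknown. State that the continuation date from 6.4 is never used for this test.

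The cost is a few sentences in the SAP and the matching lines in the dataset specifications, before programming. The data are already collected under protocol 9.5.2.

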6.4.1 Prior Therapy

Prior medication is defined as the anticancer medication stopped before the date of first dose of any study drug. Prior medication will be coded by preferred term using the latest World Health Organization (WHO) Drug Dictionary.

The safety population will be used for the analysis of prior therapy.

6.4.2 Concomitant Medications

Concomitant medication is defined as the medication ongoing at the time of the first dose of any study drug or medications started on or after the first dose of any study drug. Concomitant medications will be coded using the latest WHO Drug Dictionary. The number and percentage of patients taking concomitant medications will be tabulated by Anatomical Therapeutic Chemical (ATC) classification pharmacological subgroup and WHO standardized medication name.

The safety population will be used for the analysis of concomitant medications.

6.5 Study Drug Exposure and Compliance

The exposure to study drugs (modakafusp alfa and daratumumab) will be characterized based on safety population by summaries and descriptive statistics of duration of treatment in weeks, number of treated cycles (1, 2, 3, 4, 5, 6, 7-12, 13-18, 19-24, >24 and summary statistics), and relative dose intensity (<50%, 50% - <80%, 80% - <100%, 100%, >100%, and summary statistics).

The algorithm/calculation details will be documented in the analysis dataset specifications.

Action on Study Drug

The reason for treatment discontinuation and dose modification (e.g. dose increased, dose reduced, interrupted, withdrawn, delayed, infusion rate increased, infusion rate reduced, drug infusion interrupted) of the study drug will be summarized based on safety population.

6.6 Efficacy Analysis

All efficacy endpoints are based on investigator's assessment, if applicable.

6.6.1 Primary Endpoint Analysis

The primary efficacy endpoint for phase 2a is investigator-assessed ORR.

6.6.1.1 *Derivation of Endpoint(s)*

ORR is defined as the proportion of patients who achieved a confirmed response of PR or better per IMWG criteria.

6.6.1.2 *Main Analytical Approach*

Investigator-assessed ORR will be analyzed as the primary endpoint and calculated based on the safety population.

ORR at the primary analysis will be analyzed based on the confirmed responses, details of which is described as follows.

Confirmation of Response:

To confirm a response of sCR, CR, VGPR, PR, or MR, it requires 2 consecutive adequate assessments made at any time before the initiation of subsequent anti-cancer therapy. There is no requirement on the time interval between the two visits.

Below are some exceptions:

1. One or two consecutive occurrences of “not done” (ND) or “not evaluable” (NE) between responses can be skipped when confirming a response. For example,

PR → NE → PR: PR is considered to be confirmed in this case.

CR → ND → CR: CR is considered to be confirmed in this case.

2. Bone marrow assessments do not need to be confirmed.

Confirmation of PD:

It also requires 2 consecutive adequate assessments made at any time before the initiation of subsequent anti-cancer therapy to confirm PD. If only one PD value is recorded in the middle of responses better than PD, it will not be counted as a confirmed PD and therefore not an event for DOR, TTP, and PFS analyses. For example, the following case is not a confirmed PD:

BL → SD → PD → SD → SD → Subsequent anti-cancer therapy/End

Below are some exceptions:

- If only one PD is recorded as the last available assessment, then
 - 1) If this PD is due to imaging (plasmacytomas or bone lesion), then it can be considered as a confirmed PD.
 - 2) If this PD is the last available assessment prior to the subsequent anti-cancer therapy or is the reason for End of Treatment (EOT), then it can be considered as a confirmed PD.
 - 3) Otherwise, the PD is considered as unconfirmed.

Best Overall Response

Best overall response (BOR) is defined as the best response recorded after the first dose of study drug. The number and percentage of patients as well as corresponding 95% exact CIs with BOR in the following response categories will be summarized by dose level: sCR, CR, VGPR, PR, MR, SD, PD, and NE/ND. A list of investigator-assessed response at each visit will be provided.

Only the assessments from the start of treatment up to the earlier of confirmed disease progression or the start of subsequent anti-cancer therapy will be considered. Only subsequent systemic anti-cancer drugs are considered as anti-cancer therapy (radiotherapy and surgeries are not considered as systemic anti-cancer therapy for the purpose of this analysis). However, assessment after the treatment discontinuation will be considered. Subjects with only assessments of “Not Evaluable” or missing response will be treated as non-responders, i.e., they will be included in the denominator when calculating the percentage.

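### SAP 6.6.1.2 defines best overall response without confirmation, so the BOR table can show more or deeper responses than the confirmed ORR and CBR

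*SAP*

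**What the plan says.** SAP 6.6.1.1 states that "ORR is defined as the proportion of patients who achieved a confirmed response of PR or better per IMWG criteria". SAP 6.6.1.2 repeats the point ("ORR at the primary analysis will be analyzed based on the confirmed responses, details of which is described as follows") and sets the rule: for sCR, CR, VGPR, PR or MR, "it requires 2 consecutive adequate assessments made at any time before the initiation of subsequent anti-cancer therapy". One or two consecutive visits that are not done or not evaluable may be skipped, as in the example "PR → NE → PR: PR is considered to be confirmed in this case".

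Under its own sub-heading, the same section then says: "Best overall response (BOR) is defined as the best response recorded after the first dose of study drug". The table is more than a listing: "The number and percentage of patients as well as corresponding 95% exact CIs with BOR in the following response categories will be summarized by dose". Its rows run from sCR down to NE/ND. The following paragraph limits the time window ("Only the assessments from the start of treatment up to the earlier of confirmed disease progression or the start of subsequent anti-cancer therapy") but adds no confirmation requirement.

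Elsewhere the SAP includes confirmation in the definitions of DOR, MRD[-] CR, CBR, DCR and TTR. Protocol Appendix E Table 1 builds two consecutive assessments into sCR, CR, VGPR and PR, but not into MR.

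**The concern.** Two summaries in one section count responders by different rules, and the SAP does not say so. A reader would expect the sCR, CR, VGPR and PR rows of the BOR table to add up to ORR, and the addition of MR to give CBR. As written, they need not.

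BOR is also the table that shows depth of response by dose level, with exact confidence intervals. The plan makes no formal comparison between doses (SAP 6.1.3), and the recommended phase 2 dose is to be chosen on integrated data that include efficacy (SAP 2.0). Descriptive tables by dose are therefore what people will read. A BOR table that admits single readings could make a dose look more active, or its responses deeper, than the confirmed data support.

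**Working it through.** **1. Inputs.** About 20 patients per phase 2a arm (SAP 4.0). Two-sided 95% Clopper-Pearson intervals (SAP 6.1.3). Confirmation rule and BOR definition from SAP 6.6.1.2. The rate of unconfirmed response is not in the documents, so 0 to 3 patients per arm is assumed.

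**2. Reproduce the plan's own figures.** For x responders of n, the lower limit is the 0.025 quantile of Beta(x, n − x + 1) and the upper limit is the 0.975 quantile of Beta(x + 1, n − x). With n = 20:

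- 12/20 = 60%: 0.3605 to 0.8088, width 0.448
- 14/20 = 70%: 0.4572 to 0.8811, width 0.424
- 16/20 = 80%: 0.5634 to 0.9427, width 0.379

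All three agree with SAP 4.0. No stated figure is wrong.

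**3. Apply the two written rules to example sequences.** The SAP does not say whether the two assessments must be of the same category. Here, two consecutive assessments of PR or better count as a confirmed response, with at most two NE/ND visits skipped. The last column applies the rule proposed in the fix.

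| Sequence | BOR as written | Confirmed PR or better | BOR under the fix |
|---|---|---|---|
| SD → PR → SD → SD | PR | no | SD |
| SD → PR (last visit) | PR | no | SD |
| MR → PR → PD → PD | PR | no | MR |
| PR → NE → NE → NE → PR | PR | no | SD |
| PR → NE → PR | PR | yes | PR |
| PR → VGPR → PR | VGPR | yes | PR |

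The first four patients are responders in the BOR table and not in ORR. The last is a responder in both, but the BOR depth rests on one reading.

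**4. Direction.** Every confirmed responder has at least one recorded PR or better. If both summaries use the same assessment window, the BOR responder count is therefore at least the confirmed count.

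**5. Size in phase 2a.** Each patient with only an unconfirmed response adds 1/20 = 5 percentage points. With 12 confirmed responders (ORR 60%) and k such patients, the BOR table shows:

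- k = 0: 12/20 = 60% (0.361 to 0.809)
- k = 1: 13/20 = 65% (0.408 to 0.846)
- k = 2: 14/20 = 70% (0.457 to 0.881)
- k = 3: 15/20 = 75% (0.509 to 0.913)

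The chance of at least one such patient in an arm of 20 is 1 − (1 − q)^20, where q is the assumed proportion of patients with only an unconfirmed response. This gives 33% for q = 2%, 64% for q = 5% and 88% for q = 10%.

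**6. Phase 1.** In a dose level of 6, one such patient moves the figure by 1/6 = 16.7 points.

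**The case against.** The strongest reply is that BOR is already confirmed in effect. Its paragraph sits below the lead-in on confirmed responses, and the text after it treats not-evaluable patients as non-responders who stay in the denominator, which is ORR language. Responses follow IMWG criteria, and Appendix E requires two assessments for sCR to PR, so a site might record a category only once it is confirmed. If all sites did so, the BOR and ORR counts would agree.

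This shows that the intention is uncertain, but it does not settle the text. The PR → NE → PR example treats PR as a visit-level value that a later visit confirms. The PD rule in the same section uses *recorded* for a single unconfirmed value. A separate confirmation algorithm would be redundant if only confirmed categories were entered. Appendix E also has no two-assessment requirement for MR, whereas the SAP requires one, so even on this reading a single MR could enter the BOR table and not CBR.

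Other parts of the reply stand. BOR is not a listed primary or secondary endpoint, and no hypothesis or decision rule depends on it. Disease is assessed on Day 1 of each 28-day cycle from Cycle 2, there is no minimum confirmation interval, and assessments after treatment discontinuation count, so the gap may well be small. A listing of response by visit is planned, so differences can be traced to patients. An unconfirmed BOR is also legitimate if it is labelled as such.

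A reader might infer that the primary ORR is inflated, or that the BOR rows cannot add up to ORR. The documents support neither. ORR is explicitly confirmed, and the rows do add up whenever no patient has only an unconfirmed response.

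**Conclusion.** The point holds as a mismatch of definitions. As written, the BOR table by dose can show more responders than the confirmed ORR and CBR, or deeper responses. It cannot show fewer responders, given a common assessment window. The primary ORR and the endpoints defined on confirmed response are unaffected.

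The size rests on assumption. With 0 to 3 unconfirmed responders in an arm of 20 that has 12 confirmed, the BOR figure exceeds ORR by 0 to 15 percentage points. Nothing in the documents says where in that range, or whether within it, the trial would fall.

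The statement on direction concerns counts. The BOR paragraph names no population. SAP 5.3 makes the safety population the general efficacy set, while phase 1 ORR uses the response-evaluable population (SAP 6.6.2.1). Phase 1 percentages might therefore differ for that reason alone.

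**What to change.** Amend SAP 6.6.1.2 as follows:

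- Define BOR as the best *confirmed* response under the confirmation rule already given there.
- State in that rule that a deeper response at the adjacent assessment counts toward confirming the lower category, so that PR → VGPR confirms PR. Apply this alike to ORR, CBR and BOR.
- Assign an unconfirmed response to the best confirmed lower category, or to SD if there is none.
- Use the ORR population of each phase for BOR: response-evaluable in phase 1, safety in phase 2a.
- If an unconfirmed BOR is wanted, show it only as a separately labelled row.

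The sCR to PR rows then add up to ORR, and in phase 2a the addition of MR gives CBR. The change takes a few sentences and no new data, since response by visit is already collected and listed. The downside is that BOR figures may be slightly lower.
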